9.4.2 Analysis of the Primary Endpoints

Behavioral data analysis: Group differences (Vaping vs. TD) will be evaluated via chi-squares, independent t-tests (Primary Endpoint 1). In addition to EOT nicotine abstinence, Δ scores will be calculated for each behavioral measure (e.g. vaping frequency, emotion regulation) and will be used for within-subject analyses to characterize MBSR-related behavioral change (Primary Endpoint 2).

rsFC fMRI data analysis: Seed-based ROI whole-brain rsFC analyses between *a priori* defined hippocampal seed regions and large-scale brain networks (focusing on DMN, ECN, SN). Whole-brain regression analyses will be conducted for each seed on each individual's preprocessed data resulting in a Fisher-transformed z-value in each brain voxel (**DV**). Seed regions: Right- and left-whole and sub-region hippocampal ROI seeds such as those defined via probabilistic voxel maps created by Chase *et al.*⁹⁹ will be used for rsFC analyses. Target network identification: Hypothesis-driven seed-based analyses will be constrained to voxels within each of three functionally generated masks of large-scale brain networks (DMN, ECN, SN) identified via group independent component analysis⁶ or taken from a published atlas.

s-rsFC Analysis: Independent and Paired t tests will examine group (Vaping vs. TD) (Primary Endpoint 1) and session (Pre/Post-MBSR) (Primary Endpoint 2) effects in s-rsFC strength between each hippocampal seed and voxels within each of the 3 network masks (e.g., seed-ECN voxels).

d-rsFC Analysis: d-rsFC will be estimated using a sliding window method^{21,22} creating windowed correlation matrices, to which a k-means clustering algorithm will be applied to identify states.⁶ Independent and Paired t-tests will examine group (Vaping vs. TD) (Primary Endpoint 1) and session (Pre vs. Post-MBSR) (Primary Endpoint 2) differences in d-rsFC DVs: state occupancy and transitions.

Correlational analyses: To test relationships between MBSR-related Δ rsFC and Δ vaping behaviors and other behavioral outcomes, we will use regression analyses.

Post-hoc analyses: Post-hoc ROI seed-based whole-brain connectivity analyses will test if the regions showing mindfulness-related Δ rsFC are distinct from or overlap with regions modulated by nicotine exposure (from Primary Endpoint 1).

Abbreviated Title: Mindfulness and Teen Vaping

Version Date: 07/21/2025

NIH IRB#: IRB001855

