| | 
 - Engagement with MBSR training and post-training Craving-to-Quit app and change scores for other behavioral measure (e.g. vaping, emotion regulation). - rsFC from seeds such as dorsal anterior cingulate. |
| Study Population: | 40 nicotine vaping adolescents (13-18 years old) who vape 4-7 days per week, and 40 age, sex, race/ethnicity, SES matched typically developing (TD) adolescents with no nicotine vaping/tobacco smoking history. Participants will be recruited via online advertising, word of mouth, and from our vaping survey study. Recruitment will target the greater Baltimore area. To improve generalizability of our results, we will include youth who vape and who also smoke cigarettes (dual users) or co-use cannabis (co-MJ users) as well as those with stable psychiatric comorbidities. We will measure, control for, and exploratorily examine differences in these behaviors and groups in our analyses. |
| Phase or Stage: | This is a natural history study (comparison of teens who do and do not vape) and an open-label pilot study (comparison of teens who vape before and after MBSR training). |
| Description of Sites/Facilities Enrolling Participants: | The Biomedical Research Center of NIDA-IRP in Baltimore, MD, is the single site used for this study. |
| Description of Study Intervention: | The study intervention is a 9-week MBSR intervention once per week in-person or remotely (via an NIH approved remote platform used in compliance with policy, including HRPP Policy 303). The MBSR will be delivered to groups of 8-12 participants. Only the vaping adolescents will receive MBSR training. |
| Study Duration: | The study duration is approximately 24 months. |
| Participant Duration: | The participant duration is approximately 5.5-7 months, including baseline assessment and MRI scan 1, the 9-week MBSR intervention, and post-intervention assessment and MRI scan 2. There will also be a monthly follow-up for three months after the last MRI scan. Non-vaping participants will only complete baseline assessments and scan 1, which should take a week or less. |

Abbreviated Title: Mindfulness and Teen Vaping
Version Date: 07/21/2025
NIH IRB#: IRB001855

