Neurobiological Models of Adolescent TUD and Mindfulness Identify Overlapping Neural Circuitry. Neuroimaging studies in adults have reliably shown changes in the hippocampus, ACC, PCC, insula, supramarginal gyrus (SMG), and PFC along with DMN, ECN, and SN networks following MT and practice.^{14,51-58} These brain regions/networks show significant anatomic overlap with the brain regions/networks showing evidence of dysfunctional signaling in tobacco using youth.³⁵⁻³⁷ Of significant relevance to our proposal, impairments in hippocampal-prefrontal circuits are observed in TUD samples³⁰ and are strengthened in non-smokers following MT.^{59,60} Additionally, in d-rsFC studies, tobacco smoking adults show altered d-rsFC with fewer state transitions during abstinence^{61,62}; Conversely MT is associated with increased state transitions in non-smoking adolescents and adults.^{63,64} Taken together, these findings indicate that MT impacts neural function, connectivity, and flexibility in a manner that is opposite to the effects of chronic tobacco exposure, suggesting a possible brain mechanism via reversal or ‘normalization’ of dysfunctional networks. Janes *et al.*⁶⁵ recently showed that smartphone app-delivered MT reduced cue-induced PCC activity with the magnitude of reduction in PCC activity predicting concurrent decline in smoking in adults. Alternatively, MT could improve abstinence via compensatory or training mechanisms by strengthening connectivity in unaffected networks.

Abbreviated Title: Mindfulness and Teen Vaping

Version Date: 07/21/2025

NIH IRB#: IRB001855

In this pilot study we will investigate whether measures of s-rsFC and d-rsFC in circuits altered by chronic nicotine exposure are modulated by MT and characterize how such rsFC changes relate to vaping behavior.

Psychological Mechanisms of Mindfulness Training: Awareness & Emotion Regulation

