4 STUDY DESIGN

4.1 Overall Design

This is natural history study (comparison of vaping to non-vaping adolescents) and an open label pilot study (MBSR intervention to vaping adolescents).

This single-sight study will be carried out at the NIDA-IRP's Biomedical Research Center in Baltimore, MD.

The study will enroll up to 60 nicotine vaping youth and 60 non-vaping youth to obtain complete data on N=40 tobacco vaping youth 13-18 years old and N=40 age, sex, race/ethnicity, SES matched typically developing (TD) non-vaping/non-smoking youth. The study intervention, given to vaping teens, is a Mindfulness-Based Stress Reduction (MBSR) training. The intervention is a group-based instructor-led mindfulness-based stress reduction (MBSR) training.

Abbreviated Title: Mindfulness and Teen Vaping

Version Date: 07/21/2025

NIH IRB#: IRB001855

The MBSR intervention will consist of eight weekly 2-hour sessions and one 3-hour retreat that will take place at the NIDA BRC. Each group will consist of 8-12 participants.

Participants will be recruited online and via our concurrent vaping survey study. Only nicotine vaping youth will participate in the MBSR intervention. The vaping group will participate in one to four primary data gathering visits, all but one of which can be done virtually. The visit that will include the first MRI scan visit must take place in-person 0-3 months pre-MBSR intervention, and the second MRI scan visit will take place 0-6 weeks post-MBSR intervention. The TD non-vaping group will not participate in the MBSR intervention, and therefore will only participate in the baseline assessments (one to four virtual or in-person visits including the first in-person MRI scan). For those receiving the MBSR intervention, there will also be four monthly follow-up visits which may be administered in-person or virtually. The one at the conclusion of MBSR training may be combined with scan 2. The MBSR visits are optional, and as long as one visit is completed, the other visits if missed will not result in a deviation.

We hypothesize that teens who vape will differ from those who do not on all behavioral, cognitive and imaging measures and that the MBSR intervention will alter these measures in the vaping teens so that they will differ less from their non-vaping counterparts.

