5.6 Lifestyle Considerations

Participants will be instructed to abstain from cannabis, alcohol, and other street drugs for 24 hours and limit caffeine for 12 hours, prior to scan visits, but will be allowed to vape as usual. Abstinence will be verified on scan days via self-report, and UDT, with participants rescheduled if they test positive for THC or other drugs on UDT and fail a clinical assessment for intoxication. Participants in the vaping group will need to agree to participate in the MBSR training. One parent/guardian must be present for the consent process for participants under 18 y/o, and they will have the option to remain at NIDA while their minor is participating.

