9.4 Statistical Analyses

9.4.1 General Approach

Abbreviated Title: Mindfulness and Teen Vaping

Version Date: 07/21/2025

NIH IRB#: IRB001855

Quantitative analysis: For quantitative analysis of behavioral variables assessed at multiple time points, changes in scores across time will be presented descriptively (means, SDs) and analytically. Behavioral data encompasses scores on questionnaires assessing substance use variables, psychological functioning, and mindfulness processes. Paired t-tests will be used to examine pre- to post-treatment changes in continuous measures, and chi-squares will be used to test for pre- to post-treatment changes in categorical variables. Regression will be used to assess continuous relationships between scores on behavioral performance measures, self-report questionnaires, neuroimaging data (both pre-treatment and change from pre- to post-treatment), and outcome data.

fMRI data: resting time courses averaged from seeds of hippocampal subregions will be extracted and correlated with time courses from all other voxels in the brain on an individual level. Individual maps will be combined to obtain group level maps of connectivity from hippocampal subregions which will be compared between groups at baseline and within group pre- vs post-MBSR with t-tests.

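### The synopsis promises to control for cigarette and cannabis co-use, but the vaping-versus-control tests in 9.4 carry no covariate

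*Combined protocol and SAP*

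**What the plan says.** On who enters, the synopsis (1.1, Study Population) states that "we will include youth who vape and who also smoke cigarettes (dual users) or co-use cannabis (co-MJ users") along with youth who have stable psychiatric comorbidity. It then commits to adjustment: "We will measure, control for, and exploratorily examine differences in these behaviors and groups in our analyses".

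Section 4.1 describes the comparison group as "N=40 age, sex, race/ethnicity, SES matched typically developing (TD) non-vaping/non-smoking youth". The matching factors are therefore age, sex, race/ethnicity and SES. Section 5.1 limits controls to at most five lifetime nicotine uses and none in the 30 days before enrollment. Cannabis use is not barred in either arm; only a moderate or severe substance use disorder in the past year is.

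On analysis, 9.4.1 has the group-level maps "compared between groups at baseline and within group pre- vs post-MBSR with t-tests". Section 9.4.2 specifies for static connectivity that "Independent and Paired t tests will examine group (Vaping vs. TD) (Primary Endpoint 1) and session (Pre/Post-MBSR) (Primary Endpoint 2) effects in s-rsFC strength", and uses the same two tests for "differences in d-rsFC DVs: state occupancy and transitions". Behavioral group differences are tested by chi-square and independent t-test. Regression is reserved for brain-behavior relationships, and ANCOVA appears only in the abbreviation list. The possible subgroup factors in 9.4.7 are age, sex, race and SES, not co-use.

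**The concern.** The synopsis makes a promise that section 9 does not carry out. An independent t-test has no place for a covariate, and no sensitivity analysis takes over that role.

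This matters because the imbalance is partly built in. Under the eligibility criteria, regular cigarette smoking can occur only in the vaping arm. Cannabis use is possible in both arms, and nothing equalizes it. The rationale in 2.1 and 2.2 rests on separating vaped nicotine from smoked tobacco, which an unadjusted contrast containing dual users cannot do. The post-hoc step in 9.4.2 also takes the regions found under Primary Endpoint 1 as those modulated by nicotine exposure, so a co-use effect would carry over into the reading of the MBSR results. Leaving the model unstated also leaves the choice of covariates open until after the data are seen.

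**Working it through.** The plan gives no figure for bias from co-use, so there is none to reproduce. The inputs taken from it are 40 per group (4.1, 9.2), the two thresholds named in 9.2 (0.05 and 0.002), and the background statement in 2.2 that two-thirds of teen tobacco users are dual users. That last figure describes teen tobacco users in general, not this sample. Co-use shares and effects below are assumptions, shown as ranges.

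**Step 1. Rejection rate under a pure bias.** With no true vaping effect and a bias of b SD, the two-sample t statistic is noncentral t with 78 degrees of freedom and noncentrality b × √(40/2) = 4.472b. The two-sided critical values are 1.991 (5%) and 3.198 (0.2%).

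| Bias b (SD) | Noncentrality | Rejects at nominal 5% | Rejects at nominal 0.2% |
|---|---|---|---|
| 0.1 | 0.447 | 7.3% | 0.4% |
| 0.2 | 0.894 | 14.3% | 1.3% |
| 0.25 | 1.118 | 19.7% | 2.2% |
| 0.4 | 1.789 | 42.4% | 8.8% |

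These rates are for one test, not for the family of seed-by-network tests.

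**Step 2. What produces such a bias.** Bias = (co-use share in vapers − share in controls) × co-use effect in SD. Mixing co-users with non-users also adds a little variance, which the rejection rates here include. The assumed effect is 0.5 SD.

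| Share, vapers / controls | Bias (SD) | Rejects at 5% | Rejects at 0.2% |
|---|---|---|---|
| 25% / 0% | 0.125 | 8.5% | 0.6% |
| 50% / 0% | 0.25 | 19.3% | 2.2% |
| 67% / 0% | 0.333 | 30.6% | 4.8% |
| 67% / 10% | 0.283 | 23.3% | 3.0% |

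At 67% / 0%, an effect of 0.2 SD gives 9.0% and one of 0.8 SD gives 62.4% at nominal 5%. At 25% / 0%, the same two effects give 5.6% and 13.8%.

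**Step 3. Price of adjustment.** Take co-use as a yes/no covariate with share p in vapers, none in controls and equal groups. The squared correlation of group with co-use is p/(2 − p), so the variance of the group contrast is multiplied by 1/(1 − R²) = (2 − p)/(2 − 2p).

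- p = 0.25: 1.75/1.5 = 1.17
- p = 0.50: 1.5/1 = 1.50
- p = 2/3: 1.333/0.667 = 2.00

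The difference detectable with 80% power at 5% is 0.634 SD unadjusted. Multiplying by the square root of these factors gives 0.69, 0.78 and 0.90 SD. Any gain from lower residual variance is ignored.

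**Step 4. Size of the restricted sample.** If two-thirds of vapers were dual users, excluding them would leave 40 × 1/3 ≈ 13 vapers against 40 controls, and fewer once cannabis co-users are also removed.

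**Step 5. Matching.** Simulating matched pairs (100,000 runs per setting) and analyzing them with an independent t-test gives a type I error of 4.9, 3.8, 2.0 and 0.6% at within-pair correlations of 0, 0.1, 0.3 and 0.5. Ignoring the matching loses precision and makes the test conservative. It creates no false vaping effect.

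**The case against.** The strongest reply is that this is a small pilot with a natural-history comparison. The objective in section 3 is to characterize differences related to vaping, the hypothesis in 9.1 speaks of association, and 2.2 acknowledges the cross-sectional limitation. That lowers the severity, but it does not remove the disagreement between the synopsis and section 9.

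Several provisions limit the imbalance: moderate or severe non-tobacco use disorder is excluded in both arms, and 5.6 asks for 24 hours without cannabis before scans. Section 9.4.1 plans regressions of imaging on questionnaire scores, which include substance use. These points stand, but such regressions are not an adjusted group test. It is also fair that the larger rejection rates depend on assumed co-use and on the 5% level; 9.2 regards 0.002 as closer to a cluster-corrected threshold, where the absolute rates are much smaller.

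A reader might infer three stronger points that the documents do not support.

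- **That ignoring the matching biases the result.** Step 5 shows the opposite direction. The documents also do not say whether matching is by pair or by group.
- **That head motion is left uncorrected.** Section 9.4.2 refers to preprocessed data without describing the pipeline, and the reference list contains one noise-correction and two motion papers that the supplied text does not cite. Motion handling is unspecified, not shown to be absent.
- **That scanning vapers in their usual nicotine state is a flaw.** Section 5.6 says participants abstain from other substances "but will be allowed to vape as usual". The background statement that "tobacco smoking adults show altered d-rsFC with fewer state transitions during abstinence" concerns abstinent adults, a state this design does not impose. Urine cotinine and breath CO are taken at each scan.

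**Conclusion.** The concern holds as an inconsistency with consequences for Primary Endpoint 1. The synopsis promises control for dual and cannabis use, while 9.4.1 and 9.4.2 supply only unadjusted group tests and no sensitivity analysis. Cigarette use is confined to the vaping arm by eligibility, and co-use is not matched.

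The amount of false positive inflation is not known. It runs from almost none (5.6% for a nominal 5% at 25% co-use and a 0.2 SD effect) to severe (62% at 67% and 0.8 SD). The middle case of 50% and 0.5 SD gives about 20%. These figures assume no true vaping effect, a single test, and co-use shares and effects that the documents do not give. For cannabis the imbalance may be smaller than for cigarettes, since controls may also use it.

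This should be fixed before analysis. It is not a reason to stop or redesign a pilot whose claims are framed as associations.

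**What to change.** In 9.4.1 and 9.4.2, replace the independent t-tests for static and dynamic connectivity with a linear model of the imaging measure on group, age, sex, race/ethnicity, SES, baseline cannabis days from the 28-day TLFB, and mean framewise displacement computed from the resting scan. The matching factors are there for precision, not to remove bias.

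Prespecify a sensitivity analysis that excludes dual users and cannabis co-users, and define both categories in advance. Cigarette use has to be handled by exclusion, not as a covariate, because controls provide no overlap. Add change in framewise displacement to the pre-post model for Primary Endpoint 2, and state how motion is treated in preprocessing. A vaper-only sensitivity analysis on the cotinine already collected is optional.

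No new data are needed; the cost is plan wording and some precision. The model uses about 8 to 10 degrees of freedom out of 80 participants. Beyond that, adjusting for co-use that is rare in controls multiplies the variance of the group contrast by about 1.2 to 2.0 at 25 to 67% co-use with none in controls. The sensitivity analysis may rest on few vapers, about 13 of 40 if the two-thirds background figure applied. The plan should state these limits, and should report the unadjusted contrast beside the adjusted one so that readers can see how far the result depends on co-use.

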9 STATISTICAL CONSIDERATIONS

9.1 Statistical Hypothesis

- Primary Endpoint(s):
 - (1) Our central hypothesis is that frequent nicotine vaping in adolescents will be associated with impaired hippocampal connectivity (measured via s-rsFC) with large-scale brain networks (ECN, DMN, SN) involved in cognitive control and emotion regulation and differences in time in state and state transitions (measured via d-rsFC) between. Alternatively, our null hypothesis is that there will be no difference in the hippocampal connectivity or d-rsFC measures between groups (daily nicotine vaping adolescents and TD age-matched adolescents who do not vape).
 - (2) We hypothesize that the MBSR intervention will increase hippocampal connectivity to the ECN and normalize time in state and state transition measures in vaping adolescents, with

these Δ rsFC predicting Δ vaping behaviors. Alternatively, our null hypothesis is that there will be no change in rsFC or vaping behaviors as a result of the MBSR intervention.

- Secondary Endpoint(s):
 - (1) Descriptive statistics will be calculated to determine the feasibility and acceptability of technology-delivered MBSR, while preliminary efficacy to reduce vaping in adolescents will be assessed with t-tests.

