9.3 Populations for Analyses

- Modified Intention-to-Treat Analysis Dataset: All frequent nicotine vaping participants approved to participate in the MBSR intervention who complete the first scan day will be included in the comparison of vaping to non-vaping teens. Non-vaping teens who complete the scan will be included in this analysis.
Frequent nicotine vaping participants who completed the study intervention (regardless of number of sessions actually attended) and complete both MRI scans will be included in the pre-post imaging comparison in the vaping group. If they also complete at least one follow-up visit, they will be included in the assessment of effect of MBSR on vaping and related outcome measures.

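### The post-hoc overlap analysis uses the vapers' first scan in both maps with opposite signs, which tilts chance overlap toward apparent normalization

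*Combined protocol and SAP*

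**What the plan says.** Section 9.4.2 specifies the two primary imaging contrasts: "Independent and Paired t tests will examine group (Vaping vs. TD) (Primary Endpoint 1) and session (Pre/Post-MBSR) (Primary Endpoint 2) effects in s-rsFC strength". Its post-hoc paragraph then asks whether the regions changing with mindfulness "are distinct from or overlap with regions modulated by nicotine exposure (from Primary Endpoint 1").

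Section 9.3 settles whose scans enter. Vapers "who complete the first scan day will be included in the comparison of vaping to non-vaping teens", and those who "complete both MRI scans will be included in the pre-post imaging comparison in the vaping group". The vapers' first scan therefore feeds both contrasts. Controls have no second scan (Synopsis, section 1.1): "Non-vaping participants will only complete baseline assessments and scan 1, which should take a week or less".

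Section 4.1 expects MBSR to move the vapers' measures "so that they will differ less from their non-vaping counterparts", and section 9.1 hypothesises that it will "normalize time in state and state transition measures in vaping adolescents". Section 2.2 names normalization of vaping-related abnormalities and compensation in unaffected regions as the candidate mechanisms, possibly both at once.

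Section 9 gives no significance threshold for either map, no rule on direction, no overlap statistic and no reference distribution for the overlap.

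**The concern.** If chance makes the vapers' first scan look abnormal in some region, that region tends to enter the vaping map. The second scan, free of that particular error, tends to lie closer to the controls, so the same region also tends to enter the MBSR map with a change toward controls. This is regression to the mean acting through a shared baseline, and it needs no effect of MBSR.

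The overlap analysis is the only one in section 9 that bears on normalization versus compensation. A tilt in it favours one of the two explanations, and nothing in the plan would show that the tilt is there.

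**Working it through.** **The plan's own figures.** Section 9.2 gives 11, about 21 and 11 participants. A one-sample two-sided t-test at power 0.8 with SD = sqrt(0.5² + 0.75²/100) = 0.506 gives 11, 21 and 12, which is close agreement. These figures concern task activation in one group. The plan states no error rate for the overlap analysis.

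**Inputs.**
- 40 vapers and 40 controls with complete data (section 4.1).
- p<0.002 as an illustrative map threshold. It appears only in the power discussion (section 9.2); section 9.4.2 gives none. Two-sided tests are assumed.
- Scan-rescan correlation rho: not given. Assumed 0.3, 0.5 and 0.7, with 0.9 as a check.
- Equal variances, one region at a time. Spatial correlation and cluster correction are not modelled.

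**Correlation of the two contrasts.** Let V1 and V2 be the vaper means at the two scans and C the control mean, with unit variance and n per group.
- var(V1 - C) = 2/n
- var(V2 - V1) = 2(1 - rho)/n
- cov(V1 - C, V2 - V1) = -(1 - rho)/n
- corr = -(1 - rho) / sqrt[2 × 2(1 - rho)] = -sqrt(1 - rho)/2

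With no true effects, the expected change in a region with observed vaping difference d is -(1 - rho)/2 × d.

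**Results with no vaping effect and no MBSR effect, 40 per group.** The rates are the probability of a significant change toward controls, given a significant vaping contrast.

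| | rho 0.3 | rho 0.5 | rho 0.7 | if independent |
|---|---|---|---|---|
| Correlation | -0.42 | -0.35 | -0.27 | 0 |
| Expected reversal, share of d | 35% | 25% | 15% | 0 |
| Vaping map 0.002, change 0.05 | 25-27% | about 20% | about 14% | 2.5% |
| Both at 0.05 | 14% | 11% | 9% | 2.5% |
| Both at 0.002 | 3.3% | 2.2% | 1.2% | 0.1% |
| Share of chance overlaps pointing to reversal (both at 0.05) | 99.5% | 98.7% | 96.0% | 50% |

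The rates come from bivariate normal tail areas and were checked by simulating the t-tests; the range at rho 0.3 reflects the two methods. At rho 0.5 the mean spurious shift in regions selected at 0.002 is about 0.19 SD. At rho 0.9 the 0.002/0.05 rate is still about 7%.

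**Departures from that case.**
- A true vaping difference of 0.3 or 0.5 SD, no MBSR effect, rho 0.5: the 0.002/0.05 rate is 10% or 6%.
- Unequal numbers: the plan may "enroll up to 60 nicotine vaping youth and 60 non-vaping youth to obtain complete data on N=40 tobacco vaping youth". With 60 vapers and 60 controls in the vaping contrast and 40 vapers in the pre/post contrast, the correlation is -[(1 - rho)/60] / sqrt[(2/60) × 2(1 - rho)/40] = -0.34, -0.29, -0.22, and the rates are 20%, 15% and 11%.

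**The case against.** **How often it arises.** With no true effects, a vaping region must first appear by chance. If the vaping map is family-wise controlled at 5% and one selected region is tested for change at 0.05, a false reversal occurs in about 0.05 × 0.14 = 0.7% to 0.05 × 0.27 = 1.4% of trials. Even within such a region, roughly three quarters or more of cases show no significant reversal. This stands: a reader might infer that the analysis will show normalization when neither vaping nor MBSR does anything, and the figures do not support that. It does not remove the bias when vaping has a real effect and MBSR has none, where the rate is still 6-10% against 2.5%.

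**What the plan commits to.** The analysis is one post-hoc item in a pilot. Section 9.4.2 asks only about distinctness or overlap; it states no threshold and no rule that overlap means reversal. It also starts from the MBSR regions, whereas the main figures start from the vaping regions. These points stand as limits on the size: with both maps at 0.002 the rate is 1-3%. They do not change the direction. Sections 2.2, 4.1 and 9.1 supply the normalization reading, and almost all chance overlap points that way.

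**Rescanning controls.** A reader might infer that a second control scan would cure this. It would not. The group-by-time contrast correlates with the baseline difference at -sqrt((1 - rho)/2), which is -0.50 at rho 0.5, and the conditional rate rises to about 38%.

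**Conclusion.** The concern holds as a bias in the overlap analysis, not as a prediction of its result. For any rho below 1 the two maps have negatively correlated errors, and the plan states no safeguard. At a vaping threshold of 0.002 and a change threshold of 0.05, false reversal in a selected region is about 14% to 27% instead of 2.5%, roughly 6 to 11 times nominal (14/2.5 = 5.6; 27/2.5 = 10.8). This rests on assumed rho of 0.3 to 0.7, 40 per group, equal variances and no true effects. It is smaller with stricter thresholds for change, a real vaping difference, higher rho, or more vapers in Endpoint 1 than in Endpoint 2.

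The two primary contrasts are unaffected: each keeps its own error rate, and only their joint interpretation is distorted. The change should be made before the overlap is read as evidence on mechanism.

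**What to change.** Add one paragraph to section 9.4.2.

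1. Fix the thresholds, the overlap statistic and its direction (change toward controls or away from them).
2. Judge the overlap against a permutation null: randomly swap scan 1 and scan 2 within each vaper, then recompute both maps using the same relabelled scan 1. Vapers with only a first scan keep it. If scans are exchangeable under no pre/post change, this preserves the shared baseline. In simulation it rejected 5% and 3% of the time at a nominal 5%.
3. Base any normalization statement on that result, or on change in network means fixed in advance. Section 9.4.2 already allows masks from a published atlas. Test every listed network, not only those that differed at baseline; otherwise the selection returns.

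An alternative is to define the vaping regions from the mean of both vaper scans minus controls, in vapers with both scans. This contrast is uncorrelated with V2 - V1 and gave 2-3% false reversal in simulation. Its drawback is that it includes half of any true MBSR change.

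Leave-one-out or 10-fold region definition should not be the remedy. A region selected in every fold has a held-out mean change identical to its ordinary mean change. In simulation at rho 0.5 with leave-one-out, about 56% of regions were of this kind; they kept a shift of about 0.20 SD and about 22% false reversal.

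The cost is analysis code and the SAP paragraph; no new data or visits are needed.
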